### Table layout and format

- Placebo is the first column on the left with ACT-334441 dose groups ordered (left to right) in ascending order of dose and where appropriate the total is in the right most column.
- Placebo corresponds to the pooled subjects randomized in ‘Placebo Control (Part A)’ and ‘Placebo Control (Part B)’.

Example table layout:

| Placebo
(N=XX) | ACT-334441
0.5 mg
(N=XX) | ACT-334441
1.0 mg
(N=XX) | ACT-334441
2.0 mg
(N=XX) | ACT-334441
4.0 mg
(N=XX) | Total
(N=XX) |
|-------------------|--------------------------------|--------------------------------|--------------------------------|--------------------------------|-----------------|
| <XXXXXXXXXX>      | XX (XX.X)                      | XX (XX.X)                      | XX (XX.X)                      | XX (XX.X)                      | XX (XX.X)       |

## 10.3 Display of subject disposition, protocol deviations and analysis sets

A listing of the randomization scheme and codes is produced for randomized subjects only (ICH E3 16.1.7).

### **10.3.1 Subject disposition**

An overview of the recruitment for each country/site is presented for the FAS by treatment group and overall in a table.

An overview of the subject disposition over the course of the study is presented for the SCR by treatment group (except for Screened and Re-Screened which are only summarized for the total column) and overall in a table and comprises the number of subjects:

- Screened,
- Re-screened
- Randomized
- Treated
- Completed/ prematurely discontinued the study treatment
- Completed/ prematurely discontinued the study

#### ***10.3.1.1 Screening failures***

The number of subjects screened, randomized, failed screening and reasons for screening failure are summarized for the SCR in a table and in a listing. For subjects that fail screening twice, only the reason of the last failure is reported in the summary table. All reasons for screening failure are included in the listing together with the screening failure date.

#### ***10.3.1.2 Discontinuation from study***

For the FAS, the number and percentage of subjects who completed the study as per protocol, discontinued the study and the reasons for study discontinuation are summarized by treatment group and overall. Study completion/discontinuation details and the reasons for study discontinuation are also presented in a listing.

#### ***10.3.1.3 Discontinuation of study treatment***

For the SAF, the number and percentage of subjects who completed the study treatment as per protocol, discontinued the treatment prematurely and the reasons for study treatment discontinuation are summarized by treatment group and overall. The study treatment completion/discontinuation details and reasons for study treatment discontinuation are also presented in a listing.

### **10.3.2 Protocol deviations**

Minor and important protocol deviations are displayed in a listing. This listing includes all deviation descriptions, identifiers and categories. A second listing may be generated to list the 'other' protocol deviations. Subjects without any protocol deviations are not included in these listings.

Protocol deviations (minor and important) are summarized by treatment group and overall for the FAS. Protocol deviations are also summarized by country and treatment group for the FAS.

### 10.3.3 Analysis sets

The number and percentage of subjects included and excluded in each analysis set are summarized in a table, by treatment group and overall for the FAS.

The inclusion/ exclusion of subjects in each analysis set and the reasons are listed for all screened subjects.

In addition, the number and percentage of subjects included in the FAS but excluded from the PPS are summarized in a table as well as the reason of exclusion.

A listing is produced to present the subjects for whom the randomization code was broken at site or sponsor office. It contains the date of unblinding and the reason for unblinding.

## 10.4 Analyses of subject characteristics

### 10.4.1 Demographics

Demographic characteristics [variables defined in Section 5.2.1] are summarized by treatment group and overall, using descriptive statistics for continuous and categorical data using the FAS. Body weight and height are tabulated by gender.

A listing is produced on the SCR for the demographic characteristics. Smoking habits are presented in a separate listing for the SCR.

### 10.4.2 Baseline disease characteristics

Baseline disease characteristics [defined in Section 5.2.2] are summarized by treatment group and overall using appropriate descriptive statistics for the FAS. The variables related to the SLE relevant disease history and history of detectable ANA or anti-dsDNA testing are summarized in one table, and the variables related to modified SLEDAI-2K at baseline (active descriptors, sub-scores and scores) and PGA in a second table, and exploratory biomarkers (anti-Smith, anti-cardiolipin [IgA, IgG, IgM], anti-ribosomal P) in a third table. Listings are presented for the SCR.

### 10.4.3 Other baseline characteristics

Other baseline disease characteristics [defined in Section 5.2.3] are listed for the SCR.

### 10.4.4 Medical history

Previous and concomitant medical history (diseases/diagnoses) [defined in Section 5.2.4] are summarized separately, by treatment group and overall using the FAS. The number and percentage of subjects with at least one medical history are presented overall and by SOC and individual PT within each SOC.

SOCs/PTs are sorted by descending frequency of the number of subjects in the highest-dose group. If the frequencies of SOC or PT are the same, alphabetical order is used.

One listing is produced for the SCR.

#### **10.4.5 Previous and concomitant therapies**

Previous and concomitant therapies [defined in Section 5.2.5] are summarized separately as follows:

- ‘Previous non-SLE therapies’
- ‘Study treatment concomitant non-SLE therapies’
- ‘Previous SLE therapies’
- ‘Study treatment concomitant (Background) SLE therapies’

Number and percentage of subjects having received at least one therapy are presented overall, by ATC class (level 4) and PT within each ATC class. ATC classes are sorted by descending frequency of the number of subjects in the highest-dose treatment group. If the frequencies of ATC class are the same, alphabetical order is used. The same rule applies for PTs within ATC class.

#### **10.4.6 Other subject characteristics**

The information ‘woman of childbearing potential’ as well as the contraceptive methods and the results of the serum and urinary pregnancy tests conducted during study are presented in a listing for the SCR.

### **10.5 Analysis of study treatment exposure and compliance**

#### **10.5.1 Exposure**

Exposure characteristics for the study treatment [defined in Section 5.3.1] are summarized by treatment group using descriptive statistics for continuous and categorical data, for the SAF. The listing is produced for the SCR. The study treatment duration (days) is also tabulated by end of treatment status (completed, premature discontinuation) and overall.

Study treatment interruptions data [defined in Section 5.3.4] are summarized by treatment group using descriptive statistics for categorical data using the SAF. The reasons for treatment interruptions are included in the exposure listing.

#### **10.5.2 Compliance with study treatment**

The overall compliance to the study treatment [defined in Section 5.3.2] is summarized by treatment group using descriptive statistics for continuous and categorical data, for the FAS. The listing is produced for the SCR.

## 10.6 Analysis of the main pharmacodynamic variable(s)

This section describes the analysis of the main pharmacodynamic endpoint (i.e., change in lymphocyte count from baseline to EOT), as defined in Section 5.5.1.

The objective is to demonstrate a dose response of ACT-334441 on the lymphocyte count reduction from baseline in peripheral blood in subjects with SLE.

### 10.6.1 Hypothesis and statistical model

The null hypothesis is that there is no dose response in terms of lowering the lymphocyte count ( $p$ , which is a negative value for lowering of the lymphocyte count) from baseline to EOT, and the alternative hypothesis is the existence of a dose response:

$$H_0: p_d \geq p_{Placebo} \text{ for all doses } d = 0.5, 1, 2, 4 \text{ mg}$$

vs

$$H_1: p_d < p_{Placebo} \text{ for at least 1 dose } d = 0.5, 1, 2, 4 \text{ mg}$$

To meet the objective of demonstrating a dose response of ACT-334441 on the lymphocyte count reduction from baseline to EOT, the null hypotheses must be rejected by the test with a one-sided significance level of 5%.

### 10.6.2 Handling of missing data

In the main analysis the lymphocyte count is analyzed at EOT which for the majority of patients is Week 12. This is effectively imputation utilizing the LOCF technique i.e., using data from Week 4 (i.e. at least 21 days after the first study treatment intake) later to impute for missing Week 12 values. This is justified given the maximum effect on lymphocyte counts is expected to be achieved at 4 weeks, since in the AC-064-101 study that investigated cenerimod in healthy subjects, multiple doses resulted in mean lymphocyte count-time profiles that “plateaued” at 20–23 days of treatment in all dose groups [Cenerimod IB, section 5.2.5.2]. Subjects with missing baseline lymphocyte counts and/or no lymphocyte count at or after Week 4 are excluded from the main analysis on the PDS.

The analysis by visit includes a ‘Complete Case’ analysis at Week 12 which allows for an assessment of the effect of LOCF. The analysis on the FAS is also at EOT which uses LOCF from the last post-baseline visit with no time restriction.

### 10.6.3 Main analysis

The MCP-Mod approach consists of a set of optimized contrast tests for establishing the existence of dose-response effect. The overall strategy is described as follows:

Definition of a set of likely dose-response relations (the method allows for characteristics of the curve, such as maximum effect, to be defined at doses not studied):

- Maximum effect ( $E_{max}$ ) with 50% of the maximum effect at dose 0.2 mg

- $E_{max}$  with 50% of the maximum effect at dose 0.4 mg
- $E_{max}$  with 50% of the maximum effect at dose 1.0 mg
- Quadratic with maximum effect at dose 3.0 mg
- Sigmoid- $E_{max}$  with 50% of the maximum effect at dose 0.4 mg and 95% of the maximum effect at dose 2.0 mg.

The existence of dose-response effects is assessed with the optimized contrast tests. Dose-response effects are established at one-sided level  $\alpha=5\%$ , if the following condition on the  $p$  value holds for at least one contrast  $i$ :  $p_i := 1 - F_{\Sigma_{Dunnett}}(Z_i) < 0.05$ , where  $F_{\Sigma_{Dunnett}}$  describes the Dunnett-distribution with correlation matrix  $\Sigma_{Dunnett}$ .

The model with the minimum p-value is fitted to the data. As a sensitivity analysis, all remaining significant models are fitted to the data, and model-based dose response estimates are calculated. A table summarizing the t-statistic and adjusted p-value for each curve is presented by decreasing adjusted p-value.

A plot of the estimated dose-response curve with 95% CIs is presented along with the observed response at each dose. A table summarizing the estimates (and standard error) of each dose-response curve parameters and the AIC will also be presented.

Given established dose-response effects with MCP-Mod, PD effects are analyzed based on pairwise comparisons of reduction in lymphocyte count from baseline to EOT for each active dose level to placebo using an analysis of covariance (ANCOVA) model, adjusted for baseline lymphocyte count. Testing is done with two-sided significance level 5%. The type-1 error is controlled via a hierarchical ordering of the tests: pairwise comparison is conducted in decreasing dose order. The analysis described in this paragraph is repeated for the % change from baseline to EOT in lymphocyte counts.

This analysis is performed on the PDS.

#### 10.6.4 Supportive/sensitivity analyses

These analyses (MCP-Mod and ANCOVA) are replicated on the FAS.

The assumption that the data from part A and part B can be pooled in a single analysis [Section 10] is investigated by performing separate ANCOVAs for the two parts. Within part A, comparisons are conducted between first 3 treatment groups (0.5 mg, 1.0 mg and 2.0 mg) and placebo (Part A) and within part B between the 4th treatment group (4.0 mg) and placebo (Part B). The differences vs. placebo obtained from these models are compared with the corresponding differences from the main analysis. This sensitivity analysis is performed for the PDS and FAS.

#### 10.6.5 Subgroup analyses

Not applicable.

## 10.7 Analysis of the other pharmacodynamic variables

Quantitative descriptive statistics for absolute value, absolute change from baseline and percent change from baseline are presented by analysis visit and treatment group. These analyses are performed on the FAS.

## 10.8 Analysis of other efficacy variables

### 10.8.1.1 Exploratory disease activity endpoints

- Main analysis

For all the SLEDAI-2K variables (including number of affected joints) and the PGA variable [defined in Section 5.7.3.1], an ANCOVA model including baseline value as a covariate and treatment group as a factor is applied to the absolute change from baseline to EOT for each variable on the FAS and PPS. The difference in least squares means between each ACT-334441 dose and placebo is computed and the 95% confidence intervals for the differences are estimated.

- Secondary analysis

For the SLEDAI-2K (including number of affected joints) and PGA variables [defined in Section 5.7.3.1], separate summaries of quantitative descriptive statistics for absolute values, absolute change from baseline and percent change from baseline are presented by analysis visit and treatment group.

For modified SLEDAI-2K total score, the summaries are also presented stratified by baseline category (baseline total SLEDAI-2K score  $< 6$ , baseline total SLEDAI-2K score  $\geq 6$ , overall).

In addition, for the modified total SLEDAI-2K total score, the occurrence of an increase from baseline  $> 3$  is tabulated by analysis visit and treatment group.

The evolution of the values over time (PGA score, modified SLEDAI-2K score and number of affected joints) is provided in graphical format for each parameter from baseline to EOS visit (one figure per endpoint, one boxplot per treatment group and analysis visit).

All these analyses are performed on the FAS.

Listings are produced on the SCR. For PGA and SLEDAI-2K score, it displays the absolute values, the absolute change and the percent change from baseline to each post-baseline assessment, the values taken into account for the analysis are flagged.

In addition, for the modified SLEDAI-2K, the value at each analysis visit for each descriptor is included in a listing.

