#### **8.3.2 Visit 8 and Visit 9– follow-up (telephone contact visits)**

Eleven weeks  $\pm$  5 days and 16 weeks  $\pm$  5 days, after the last dose of study drug has been taken, telephone calls will be made and include:

- Recording of SAEs
- Urine pregnancy test for WOCBP (performed at home prior to telephone contacts with test kits dispensed at Visit 7 – EOS)

Note that the data reported at these visits will not be entered in the eCRF. Results of the urine pregnancy tests must be reported in the source data. SAEs will be reported to Global Drug Safety and will be presented separately in the Clinical Study Report.

#### **8.4 Unscheduled visits (U1, U2...)**

Unscheduled visits may be performed at any time during the study. These visits include (but are not limited to) those performed due to safety (e.g., occurrence of an AE, laboratory abnormalities), and/or SLE disease exacerbations (e.g., renal flare).

The date of the visit and the reason for such visits as well as any data related to study assessments performed at unscheduled visits will be recorded in the eCRF.

During an unscheduled visit, the following assessments must be performed:

- Recording of changes in concomitant medications and background SLE therapies since last visit
- Recording of AEs/SAEs

Additional assessments may be performed at the discretion of the investigator including but not limited to:

- Abbreviated physical examination
- SLEDAI-2K and PGA
- SBP/DBP
- 12-lead ECG
- Hematology (including coagulation tests) and blood chemistry
- Urine pregnancy test (for WOCBP)
- ANA, anti-dsDNA antibodies, complement C3 and C4
- Urine protein-to-creatinine ratio
- Urinalysis

Depending on the reason for the unscheduled visit (e.g., AE), additional assessments will be performed based on the judgment of the investigator, and the results will be recorded in the eCRF. For the additional assessments performed during unscheduled visit which are not part of the standard study assessments, results are not to be reported in the eCRF. However, any clinically relevant abnormalities detected must be reported as an AE or SAE as appropriate in the corresponding Adverse Event form of the eCRF. After an

unscheduled visit, the regular scheduled study visits must continue according to the planned visit and assessment schedule.

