#### 4.3 Clarifications concerning endpoint definitions and related variables or statistical methods

##### 4.3.1 Analysis visits

To allow analysis of data at the relevant planned (scheduled) visits, all recorded assessments, including unscheduled ones, are assigned to the most appropriate analysis visit according to the best fitting time-window for that visit (more details are given in Section 11). The visit windows are based on the number of days from first study treatment intake and from last study treatment intake.

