##### Additional variables/endpoints related to SLEDAI

For the modified SLEDAI-2K score, additional variables/endpoints are added:

- Value at baseline categorized as ‘ $\geq 6$ ’ and ‘ $< 6$ ’;
- Occurrence of an increase from baseline  $> 3$  at each post-baseline analysis visit.

*Rationale for change:*

More granularity in the SLEDAI-2K categories is provided to better describe the disease severity and to assess lupus flares during the study.

A SLEDAI score of 6 is considered to be clinically relevant, because a score of  $> 5$  has  $> 50\%$  probability of requiring lupus-directed therapy [Nuttall 2013]. In turn, a SLEDAI-2K of  $< 6$  is considered as mild disease, whereas a SLEDAI-2K of  $\geq 6$  points corresponds to moderate or severe SLE disease activity.

Reduction in the flare rate is a useful clinical trial endpoint even in a small trial. An increase in the global SLEDAI-2K score of  $> 3$  points is considered to distinguish SLE patients with persistently active disease versus those having a disease flare [Nuttall 2013, Nikpour 2009].

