#### 5.7.3.1 *Exploratory disease activity variables*

- Modified Systemic Lupus Erythematosus Activity Index-2000 (SLEDAI-2K)

The following endpoints are defined:

- Absolute values, absolute change and percent change in modified total SLEDAI-2K score from baseline to each post-baseline analysis visit (including EOT);
- Absolute values, absolute change and percent change in SLEDAI-2K mucocutaneous subscore, musculoskeletal subscore, and combined mucocutaneous and musculoskeletal subscores from baseline to each post-baseline analysis visit (including EOT).

In addition, for the modified total SLEDAI-2K score, the following endpoints are defined:

- Occurrence of an increase from baseline of > 3.

In addition, for subjects presenting with arthritis, the following endpoint is defined:

- Number of affected joints at baseline;
- Number of affected joints and change from baseline to each post-baseline analysis visit.

- Physician's Global Assessment of disease (PGA)

The following endpoints are defined:

- Absolute value, absolute change and percent change in PGA score from baseline to each post-baseline analysis visit (including EOT).

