#### 11.1.2 Retests and multiple assessments in the same visit window

Unless specified otherwise, for findings (e.g., 12 lead ECG, laboratory data), in the case of multiple results in the same analysis visit/ time point, the results included in summary tables are selected according to the following rules:

- Prior to first study drug administration

For the same parameter and the same subject, only the latest non-missing result available prior to first study drug administration is retained for analysis.

- After first study drug administration

For the same parameter and the same subject in the same visit window, only the result of the first non-missing assessment (closer to the target day) is retained for analysis. In case of equidistant values from the planned time point, the last assessment is considered for the analyses. Where multiple assessments fall on the same day, then the latest is used.

The records to be taken into account in the analysis are to be flagged (the variable **Analysis Record Flag** is defined to support the selection of the right assessment). All results are listed.

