## 11.2.18 Questionnaires Data

This dataset contains information from the Questionnaire (QS) Domain and its supplemental domain, mapped into a basic data structure.

- Modified Systemic Lupus Erythematosus Activity Index-2000 (SLEDAI-2K)

The QS Domain contains the 23 individual descriptors but also the total SLEDAI-2K score and the combined musculoskeletal and mucocutaneous manifestations subscores.

Two additional parameters are created:

The **Mucocutaneous Score** is defined as the weighted sum of each of the individual descriptors for the applicable organ class, i.e. mucosal ulcers, rash, and alopecia. It can be computed by summing up the standardized result for each descriptor.

The **Musculoskeletal Score** is defined as the weighted sum of each of the individual descriptors for the applicable organ class, i.e. arthritis and myositis. It can be computed by summing up the standardized result for each descriptor.

The usual **Baseline, Absolute value at each post-baseline analysis visit, Absolute and percent change from baseline to each post-baseline analysis visit** variables are defined for the total score and for the 3 sub-scores based on the numeric result (standardized).

The **Baseline Category** is defined, for the total score only, as ‘ $\geq 6$ ’ and ‘ $< 6$ ’.

The **Occurrence of an increase from baseline  $> 3$ ,  $> 6$ ,  $> 12$**  are defined, for the total score only, at each visit, based on the absolute change from baseline.

[figure not shown]
- Physician's Global Assessment of disease (PGA)

[figure not shown]
The QS Domain contains the original value recorded on the eCRF (length from 0 to 100 mm) and the standardized value (from 0.00 to 3.00).

The usual **Baseline, Absolute value at each post-baseline analysis visit, Absolute and percent change from baseline to each post-baseline analysis visit** variables are defined based on the numeric result (standardized).

- 36-Item Short Form Health Survey v2 (SF 36v2TM) questionnaire

The QS Domain contains the original value (decode format) recorded on the eCRF (eg., ‘Excellent’, ‘All of the time’) and the standardized value as specified in the SF-36 v2 manual.

The **Analysis value (Character)** is defined for the ‘parent records’ only and contains the Finding in Original Units.

The **Baseline value (Character)** is defined for the ‘parent records’ only and contains the Finding in Original Units.

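### The SLEDAI-2K flare endpoint is tabulated only by visit, from one score per window: no per-subject occurrence is planned, and unscheduled flare scores after Day 21 will often reach only the listings

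*SAP*

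**What the plan says.** SAP 4.3.2 introduces the > 3 rise in modified SLEDAI-2K as an addition to the protocol. Its rationale is to describe flares over the course of the study, and it states: "Reduction in the flare rate is a useful clinical trial endpoint even in a small trial". There the endpoint is attached to each post-baseline analysis visit. SAP 5.7.3.1 lists it with no time frame: "Occurrence of an increase from baseline of > 3". In SAP 11.2.18 the flags "are defined, for the total score only, at each visit, based on the absolute change from baseline". In SAP 10.8.1.1 the only display is that the occurrence "is tabulated by analysis visit and treatment group".

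Records reach that table in two steps. Under SAP 4.3.1, "all recorded assessments, including unscheduled ones, are assigned to the most appropriate analysis visit according to the best fitting time-window for that visit". Then, under SAP 11.1.2, within a window "only the result of the first non-missing assessment (closer to the target day) is retained for analysis". Ties are settled as follows: "In case of equidistant values from the planned time point, the last assessment is considered for the analyses".

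Protocol 8.4 gives, among the reasons for an unscheduled visit, safety "and/or SLE disease exacerbations (e.g., renal flare"), and lists SLEDAI-2K among the assessments the investigator may do there. Protocol 7.4.1 schedules SLEDAI-2K at every visit except Week 2.

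**The concern.** A flare is an event that can occur between visits. A by-visit table answers a different question: how many subjects are more than 3 points above baseline at a given visit. Its rows cannot be added up to subjects who ever flared, because a lasting flare appears in several rows and different subjects may flare at different visits.

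In addition, the score most likely to catch a flare, one taken because the subject worsened, competes with the scheduled score in its window and usually lies further from the target day. What is at stake is whether the study can report what SAP 4.3.2 says the endpoint is for. Disease activity is a stated exploratory objective. A flare proportion assembled from listings after unblinding would be post hoc.

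**Working it through.** The documents give no flare rate, flare sample size or flare power, so there is no plan figure to reproduce. The check applies the SAP's own selection rules.

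**Inputs.** SAP Table 11 windows and targets: Week 2, Days 2-21 (target 15); Week 4, Days 22-42 (29); Week 8, Days 43-70 (57); Week 12, Days 71-105 (85). These total 20 + 21 + 28 + 35 = 104 days. Scheduled SLEDAI-2K: Weeks 4, 8 and 12 (Protocol 7.4.1). Visit window: ± 5 days (protocol Table 1). Recall: 10 days (Protocol Appendix 6).

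**Rule.** With an unscheduled score on day d, a scheduled score on day s and a target t, the unscheduled score is selected if |d − t| < |s − t|, or if the two are equal and d > s. The day d = s is counted as selected. In the Week 2 window no SLEDAI-2K is scheduled, so all 20 days are selected.

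**Assumption.** All three scheduled visits are shifted from target by the same number of days.

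| Shift | Not selected: Week 4 + Week 8 + Week 12 | Of all 104 days | Of Days 22-105 (84 days) |
|---|---|---|---|
| 0 | 20 + 27 + 34 = 81 | 78% | 96% |
| 5 days early | 10 + 17 + 24 = 51 | 49% | 61% |
| 5 days late | 11 + 18 + 25 = 54 | 52% | 64% |

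Averaged over shifts from −5 to +5, 63% of the 104 days are not selected (66 days, or 66/84 = 79% of Days 22-105). If a day within the 10-day recall before a scheduled score is treated as still captured, 44% of the 104 days on average are neither selected nor covered.

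**Up to EOT only.** Some days in the Week 12 window follow the Week 12 visit. Leaving these out:
- On target: 81 − 20 = 61 of Days 22-85 (64 days), 95%.
- 5 days early: 51 − 15 = 36 of Days 22-80 (59 days), 61%.
- 5 days late: 54 − 15 = 39 of Days 22-90 (69 days), 57%.

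**Would the next scheduled score still show the flare?** Take visits 28 days apart, onset uniform between them and a flare lasting L days. The probability is min(1, (L + 10)/28): 17/28 = 61% for L = 7, 20/28 = 71% for L = 10 and 24/28 = 86% for L = 14. So 14% to 39% would not show. The durations are assumed. Protocol 5.2.4 gives 14 days only as the limit on a temporary corticosteroid increase. The figure applies only where an unscheduled score was taken and displaced.

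**By-visit rows against subjects.** As an illustration, suppose Weeks 4, 8 and 12 each show 2 of 12 subjects. The number with at least one rise > 3 could be anything from 2 (17%, the same two each time) to 6 (50%, all different). The planned table cannot tell these apart.

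**The case against.** A reader might infer that unscheduled scores are discarded. They are not. SAP 4.3.1 and 11.1.1 assign them to windows, and they are selected when nearer the target, when tied and later, or when alone. That normally covers all of Days 2-21 and any missed visit. Nor are flares lost from the record: SAP 10.8.1.1 lists every score with the analysed ones flagged.

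A reader might also infer that a dose-placebo comparison is pulled towards no difference. The SAP plans no test, difference or interval for this endpoint. The planned comparison is an ANCOVA on change to EOT.

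It is fair to say that a by-visit table matches the by-visit definition in 4.3.2, and that a lasting flare seen at several visits is ordinary prevalence, not double counting. Other routes capture some flares. Premature discontinuation brings an EOT visit within 7 days with SLEDAI-2K (Protocol 5.1.9 and 8.2.4), and the FAS EOT record takes the latest value (SAP 11.1.1). AEs marked as SLE flare (SAP 5.8.5.2) enter the general treatment-emergent tables, although section 10.9 gives them no total of their own. The public SAP shows no list of outputs under section 13, so absence is judged from section 10.

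One score per window also limits unequal ascertainment. Unscheduled visits happen for safety reasons too, so an any-time flag gives subjects with more visits more chances to be counted.

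These points limit the claim but do not answer it. Displacement after Day 21 is real, a listing is not a summary, and no per-subject occurrence is specified. For safety abnormalities SAP 10.9 uses the nearest value in by-visit tables and all data for summaries over the study period. That second kind of summary is what flare lacks.

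**Conclusion.** The point holds in a limited form. The SAP adds an endpoint to describe flares and supports it with the flare rate, but plans no per-subject occurrence. Its one-score rule will often keep an unscheduled exacerbation score after Day 21 out of the only table. In the three scenarios worked, that affects 57% to 95% of possible days between Day 22 and EOT.

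These are shares of calendar days under a common visit shift. They are not shares of flares, and the documents give no basis for a flare count. The 14% to 39% is illustrative and should not be read as a loss rate under the SAP.

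The endpoint is exploratory and neither the main pharmacodynamic analysis nor any planned test changes. This is an inexpensive improvement, not a correction on which the study's conclusions depend.

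**What to change.** Add to SAP 10.8.1.1: by treatment group on the FAS, the number and percentage of subjects with at least one increase > 3 from baseline in modified SLEDAI-2K between first dose and EOT, using all post-baseline assessments including unscheduled ones, with a 95% CI. The Clopper-Pearson method in SAP 9.1.1 serves. Show the number of SLEDAI-2K assessments per group beside it, so that unequal ascertainment is visible, and keep the by-visit table as support.

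The cost is one derived subject-level flag and one table from data already collected. Intervals will be wide: with 0 of 12 subjects the upper limit is 1 − 0.025^(1/12) = 26%. The one drawback is that more unscheduled visits give more chances to be counted. Blinding should keep this small, and the assessment counts show it.
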